11.2.2. Adverse Events of Special Interest (AESI)

Adverse events of Special Interest are pre-specified as the following (PTs):

- 1. Aspartate aminotransferase increase (CTCAE Grade \geq 3)
- 2. Alanine aminotransferase increase (CTCAE Grade \geq 3)
- 3. Presyncope (any CTCAE Grade)
- 4. Syncope (any CTCAE Grade)
- 5. Ventricular arrhythmia (CTCAE Grade \geq 3)
- 6. Cardiac failure (CTCAE Grade \geq 3)
- 7. Sudden death
- 8. Seizure (any CTCAE Grade)
- 9. Hyperglycemia (CTCAE Grade \geq 3)

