4.3.3 Exclusion Criteria

- 1. Patient with other forms of lung cancer (e.g., small cell, neuroendocrine tumors).
- 2. Woman who is pregnant or breast-feeding.
- 3. Reversible causes of reduced food intake, as determined by the Investigator*. These causes may include, but are not limited to:
 - a. NCI CTCAE Grade 3 or 4 oral mucositis,
 - b. NCI CTCAE Grade 3 or 4 GI disorders [nausea, vomiting, diarrhea, and constipation],
 - c. mechanical obstructions making patient unable to eat, or
 - d. severe depression.
- 4. Patient undergoing major surgery (central venous access placement and tumor biopsies are not considered major surgery) within 4 weeks prior to randomization. Patient must be well recovered from acute effects of surgery prior to screening. Patient should not have plans to undergo major surgical procedures during the treatment period.
- 5. Patient currently taking androgenic compounds including but not limited to testosterone, testosterone-like agents, oxandrolone;

Megestrol acetate;

Corticosteroids [for details see Section 5.13.1];

Olanzapine, mirtazapine (however, long-term use of mirtazapine for depression for at least four weeks prior to screening is allowed);

Dronabinol;

Marijuana (cannabis), or

Any other prescription medication or off-label products intended to increase appetite or treat unintentional weight loss^{*}

- 6. Patient with pleural effusion requiring thoracentesis, pericardial effusion requiring drainage, edema or evidence of ascites^{*}
- 7. Patient with uncontrolled or significant cardiovascular disease, including:
 - a. History of myocardial infarction within the past 3 months
 - b. A-V block of second or third degree (may be eligible if currently have a pacemaker)
 - c. Unstable angina
 - d. Congestive heart failure within the past 3 months, if defined as NYHA class III-IV

- e. Any history of clinically significant ventricular arrhythmias [such as ventricular tachycardia, ventricular fibrillation, Wolff-Parkinson-White (WPW) syndrome, or torsade de pointes]
- f. Uncontrolled hypertension (blood pressure >150 mm Hg systolic and >95 mm Hg diastolic)
- g. Heart rate < 50 beats per minute on pre-entry electrocardiogram and patient is symptomatic.*
- 8. Patient on drugs that may prolong the PR or QRS interval durations, such as any of the antiarrhythmic medications Class I (Fast sodium (Na) channel blockers)
- 9. Patient unable to readily swallow oral tablets^{*}.

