8.1.2.1 Adverse Events of Special Interest (AESI)

Adverse Events of Special Interest are defined as pre-specified events, under monitoring by the Sponsor and for which detailed information by the Investigator may be needed.

In this study protocol AESIs are considered the following:

- 1. AST increase (CTCAE $G \ge 3$)
- 2. ALT increase (CTCAE $G \ge 3$)
- 3. Presyncope
- 4. Syncope
- 5. Ventricular arrhythmia (CTCAE $G \ge 3$)
- 6. Heart failure (CTCAE $G \ge 3$)
- 7. Unexplained sudden death
- 8. Seizure (any CTCAE Grade)
- 9. Hyperglycemia (CTCAE $G \ge 3$)

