9.4.6 Safety Analysis

The safety analysis will be performed on the Safety population.

Clinical evaluations for safety assessments will include adverse events (AEs) assessment, physical examination (PE), vital signs, 12-lead electrocardiogram (ECG), laboratory test (hematology, blood chemistry, urinalysis), Tumor assessments, Overall Survival.

Adverse events, 12-lead ECGs, vital signs, and laboratory assessments will be summarized by treatment group. All safety summaries and analyses will be performed based on the Safety Set. All safety and tolerability data will be listed. A treatment-emergent AE is one with an onset date on or after the date of the first dose of the study drug and up to Visit 11 (Day 183 +3 days) the last study visit.

AEs will be coded using Medical Dictionary for Regulatory Activities (MedDRA) dictionary (the version will be provided in the SAP and in the Data Management Plan [DMP]) to give a preferred term (PT) and a system organ class (SOC) for each event. The number and percentage of patients who experienced at least one TEAE, drug-related TEAE (defined as AEs with relationship classified by the investigator as definitely, probably, possibly, unassessable or missing), serious TEAE, serious related, severe TEAE (i.e. TEAE with CTCAE grade \geq 3), AESI (as described below), and the number and percentage of patients withdrawn due to TEAE will be summarized by treatment arm.

For each SOC and PT, summaries will be made with respect to the proportion of patients having at least one occurrence of that event during the study and the total number of events. The incidence of TEAEs in each treatment arm will be presented overall, by SOC and PT, and by additional grouping by severity according to the CTCAE grade and relationship to the study treatment. Tables of TEAEs will be presented by relationship to study drug. Additional tables including any relationship to study drug will be presented.

Adverse events of Special Interest are described in Section 8.1.2.1.

No formal test will be used for "between groups" comparison. All AEs will be listed.

Physical examination results at screening will be summarized in a frequency table (normal/abnormal). Results and relevant findings will be listed.

Vital signs will be summarized by treatment using descriptive statistics for absolute values and change from baseline (i.e., last value before first study drug intake).

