1. LIST OF ABBREVIATIONS

5-IASS	5-item Anorexia Symptom Subscale score
ACS	Anorexia/Cachexia Subscale
ADaM	Analysis Data Model
AE	Adverse Event
AESI	Adverse Event of specific interest
ALT	Alanine Aminotransferase
ANAM	Anamorelin
ANCOVA	Analysis of Covariance
ANOVA	Analysis of Variance
AST	Aspartate Aminotransferase
BDRM	Blinded Data Review Meeting
BL	Baseline
BMI	Body Mass Index
BP	Blood Pressure
CDISC	Clinical Data Interchange Standards Consortium
CCR	Composite clinical response
CI	Confidence Interval
CRF	Case Report Form
CSR	Clinical Study Report
CTCAE	Common Terminology Criteria for Adverse Events
ECG	Electrocardiogram
ECOG	Eastern Cooperative Oncology Group
ePRO	Electronic Patient Reported Outcome
EOS	End of Study
EOT	End of Treatment
FAACT	Functional Assessment of Anorexia/Cachexia Treatment
FACIT	Functional Assessment of Chronic Illness Therapy
FACIT-F	Functional Assessment of Chronic Illness Therapy-Fatigue
FACIT-G	Functional Assessment of Cancer Therapy - General
FAS	Full Analysis Set
FDA	Food and Drug Administration
FU	Follow up
GCP	Good Clinical Practices
GGT	Gamma glutamyl transferase
HAS	Hunger Assessment scale
HbA1c	Hemoglobin A1c
HLGT	High Level Group of Terms
HLT	High Level Term
HR	Hazard Ratio
IC	Informed Consent
ICH	International Conference on Harmonization

HELSINN

T AN001 Effective Date 25 JUL 2022 Approved Version 2.00

ISS	Integrated Summary of Safety
ITT	Intent-to-Treat
IWRS	Interactive Web Response System
Kg	Kilogram
LDH	Lactate dehydrogenase
LLT	Lowest Level Term
LS	Least Squares
MAR	Missing at Random
max	Maximum
MedDRA	Medical Dictionary for Regulatory Authorities
MI	Multiple Imputation
mg	Milligram
min	Minimum
MNAR	Missing not at Random
NSCLC	Non-Small Cell Lung Cancer
OR	Odds Ratio
PD	Protocol Deviation
PE	Physical Examination
PGIC	Patient Global Impression of Change
PGIS	Patient Global Impression of Severity
PP	Per protocol
PT	Preferred Term
Q1	25 th percentile or lower quartile
Q3	75 th percentile or higher quartile
QD	Once daily
QC	Quality Control
RECIST	Response Evaluation Criteria in Solid Tumors
SAE	Serious Adverse Event
SAP	Statistical Analysis Plan
SAS	Statistical Analysis System
SD	Standard Deviation
SDTM	Study Data Tabulation Model
SE	Standard Error
SI	Standard International
SMQ	Standardized MedDRA Queries
SOC	System Organ Class (in MedDRA)
TEAE	Treatment-Emergent Adverse Event
TEAESI	Treatment-Emergent Adverse Event of Special Interest
TLFs	Tables, Listings and Figures
TOI	Trial Outcome Index

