11.2. Adverse Events

AEs will be coded using Medical Dictionary for Regulatory Activities (MedDRA) dictionary (version 22.0) to assign a preferred term (PT) and a system organ class (SOC) for each event.

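### SAP 11.2.2 ties the AESI ventricular arrhythmia to one preferred term, so a grade 3 or higher event coded to a more specific arrhythmia could drop out of the by-arm AESI count

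*SAP*

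**What the plan says.** Protocol 8.1.2.1 sets the definition at the level of events: "Adverse Events of Special Interest are defined as pre-specified events, under monitoring by the Sponsor". It names nine, among them ventricular arrhythmia of CTCAE grade 3 or above. Protocol 9.4.6 plans the by-arm summary ("AESI (as described below), and the number and percentage of patients withdrawn due to TEAE will be summarized by treatment arm") and points back for the definition: "Adverse events of Special Interest are described in Section 8.1.2.1".

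SAP 11.2.2 restates the nine entries under the words "Adverse events of Special Interest are pre-specified as the following (PTs". Ventricular arrhythmia stands there as a single term with the same grade limit and no component terms. SAP 11.2 uses MedDRA 22.0 "to assign a preferred term (PT) and a system organ class (SOC) for each event". SAP 11.2.3 includes treatment-emergent AESIs in the overall adverse event summary by treatment group, and SAP 11.2.6 adds an AESI table by arm and a separate listing.

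Protocol 4.3.3, exclusion criterion 7e, shows what the protocol itself understands by ventricular arrhythmia: "Any history of clinically significant ventricular arrhythmias [such as ventricular tachycardia, ventricular fibrillation, Wolff-Parkinson-White (WPW) syndrome, or torsade de pointes".

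**The concern.** The protocol promises a count of patients with an event. The SAP delivers a count of patients with one dictionary term. If a tachycardia, fibrillation or torsade de pointes of grade 3 or above is coded to its own preferred term, the literal SAP rule does not recognise it as this AESI, although the protocol would.

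What is at stake is the count of unique patients for the grouped event. Under SAP 11.2.3 a patient is counted once for each applicable preferred term, so adding preferred term rows can count the same patient twice and does not reproduce that figure. It could be rebuilt from the patient listings, but SAP Section 3 places all analyses after unblinding, so any term list first drawn up then would be chosen with treatment assignment known.

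**Working it through.** The plan gives no figure to reproduce. The check is a reading of the rule, followed by a scale for its possible effect.

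**Step 1: apply the rule.** Under SAP 11.2.2 an event is this AESI only if its preferred term is ventricular arrhythmia and its grade is 3 or above. Suppose a treatment-emergent event of grade 3 or above carries one of these terms:

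| Coded term | In AESI count, table and listing | In grade 3 or higher SOC/PT table (SAP 11.2.3) | In adverse event listing |
|---|---|---|---|
| Ventricular arrhythmia | yes | yes | yes |
| Ventricular tachycardia | no | yes | yes |
| Ventricular fibrillation | no | yes | yes |
| Torsade de pointes | no | yes | yes |

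Exclusion 7e also names WPW syndrome. Of its four named conditions, 0 are AESI terms in SAP 11.2.2. The point does not depend on WPW syndrome: without it the result is 0 of 3.

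**Step 2: look for anything that widens the term.**
- "Standardized MedDRA Queries" appears in the SAP abbreviation list, as do the two higher-level MedDRA groupings (HLT and HLGT). The SAP text applies none of them to AESIs.
- No preferred term list, case report form flag, adjudication step or blinded term review is described for AESIs.
- By contrast, SAP 8.8 defines fluid retention by five preferred terms, confirmed after a review at the blinded data review meeting (BDRM). That list carries the general term oedema and the specific term peripheral oedema as separate entries.
- SAP Section 13 records no change to the AESI definition.

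**Step 3: scale, for illustration only.** SAP 4.1 gives 318 patients randomised 1:1. Assuming an even split, 318/2 = 159 per arm; the Safety Set may be smaller. One missed patient is 1/159 = 0.63 percentage points.

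Assume that 0 to 3 patients in an arm have a qualifying event coded only to a specific term, and that none is coded to the general term. The AESI row then shows 0/159 in every case. The exact (Clopper-Pearson) two-sided 95% upper limit is the value of p at which P(X ≤ x) = 0.025 for X binomial with n = 159. For x = 0 it is 1 − 0.025^(1/159) = 2.29%.

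| Patients with the grouped event (assumed) | Rate | 95% upper limit |
|---|---|---|
| 0 | 0% | 2.29% |
| 1 | 0.63% | 3.45% |
| 2 | 1.26% | 4.47% |
| 3 | 1.89% | 5.41% |

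The SAP plans no confidence limits for adverse event rates. The limits only show how much a small count can matter.

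**The case against.** The strongest reply is that the mechanism depends on coding that the documents do not show. Nothing supplied says how MedDRA 22.0 codes these arrhythmias, and exclusion 7e is an eligibility rule on history, not a coding rule. This stands: the undercount is possible, not demonstrated. Criterion 7e also excludes patients with such a history, and no event rate is given.

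A second reply is that the SAP entries may be loose labels. The SAP says that it follows the protocol, and Section 13 lists no AESI change. Against this, the SAP replaced several protocol names with dictionary-style ones (heart failure became cardiac failure, and AST and ALT were spelled out) and then called the entries preferred terms. The literal reading is the natural one.

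A third reply is that existing outputs limit the harm, and largely they do. SAP 11.2.3 gives grade 3 or higher events by system organ class and preferred term, with each patient counted once per class. SAP 11.2.4 adds maximum grade by preferred term, and SAP 11.5 gives ECG shift and outlier tables that do not depend on coding. A count at preferred term level is still pre-specified; only the grouped count is absent. Because the arrhythmia names in 7e are already in the protocol, a later grouping on those names would not be a free choice after unblinding.

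Fourth, the mock tables (SAP 12.5) are a separate document, and the BDRM minutes were not supplied. Either may hold a term list. SAP 11.2.2 cites none.

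Fluid retention is also only a partial precedent: its terms feed a sensitivity analysis of a co-primary endpoint, whereas AESIs feed descriptive tables. It shows that the method was available, not that it was owed here.

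**Conclusion.** The point holds for ventricular arrhythmia, as a minor issue. As written, the SAP rule is narrower than the protocol's event and can leave a qualifying arrhythmia out of the by-arm AESI count, table and listing. The size cannot be derived and may be zero. The 0.63 percentage points per patient rests on an assumed 159 per arm, and the counts of 0 to 3 are assumed.

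Three stronger readings are tempting, and the documents do not support them.
- A reader might infer that serious arrhythmias disappear from the report. They do not: they remain in the general and grade 3 or higher tables and in the listings. Safety is descriptive, and no efficacy result or formal test changes.
- A reader might infer that the AESI rate will be understated. That needs both events and a coding split, and the documents show neither.
- A reader might extend the point to cardiac failure and hyperglycemia. For cardiac failure there is only a difference of wording, such as "Congestive heart failure within the past 3 months, if defined as NYHA class III-IV" in exclusion 7d. For hyperglycemia, protocol 1.3 speaks of reactions related to increased blood glucose, without grades or terms, and SAP 11.3 summarises glucose by laboratory grade in any case. Neither is a supported example.

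**What to change.** In SAP 11.2.2, define ventricular arrhythmia by a preferred term list that includes at least the specific arrhythmias named in exclusion 7e, or by a narrow standardised query. Confirm it in a blinded term review. Keep the protocol's CTCAE limit. Report unique patients for the group by arm, with the single preferred terms as sub-rows, and record the change in Section 13. The same review may check cardiac failure and hyperglycemia, with no presumption that they need a list.

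If a list already exists in the mock tables or BDRM minutes, citing it in 11.2.2 is enough. If unblinding has occurred, add the grouped row and label it post hoc.

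The cost is a term review for one event, one lookup table in programming and one line in Section 13. The AESI count may rise in either arm by an amount that cannot be known in advance.

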11.2.3. Summaries of Adverse Events

A summary table reporting the total number of events, the total number of patients and the percentage of patients experiencing at least one of the following:

- Treatment-emergent adverse events (TEAEs)
- Drug-related TEAEs
- Serious TEAEs (SAEs)
- Drug-related SAEs
- TEAE CTCAE ≥ grade 3.
- TEAEs leading to treatment discontinuation
- Drug-related TEAEs leading to treatment discontinuation,
- Treatment-emergent AEs of special interest
- AEs with outcome Deaths

will be created by treatment group.

Drug-related TEAE are defined as AEs with relationship classified by the investigator as definitely, probably, possibly, unassessable or missing.

Each of the categories reported above will also be summarized in separate tables by SOC and PT:

By decreasing frequency for SOC;

By decreasing frequency for PT within the SOC;

Business & Decision

Life Sciences

Each summary table will be created by treatment group and overall.

For all adverse events, data will be prepared classifying events using MedDRA dictionary with respect to preferred term and SOC by treatment group.

Patients will be counted only once at the SOC level and will be counted once for each applicable preferred term; the total number of events will be presented for each SOC/PT.

11.2.4. Summaries of Adverse Events by Maximum CTC grade Severity

At individual patient level, the maximum CTC grade describes the worst grade experienced by a patient at any point in the treatment, irrespective to the AEs.

At a SOC/PT level, if a subject has multiple AEs with same preferred term the maximum CTC grade for that PT is used in the analysis.

If an AE has no grading, grade 3 is assigned; grade 4 or 5 will be assigned only if lifethreatening consequence or death respectively will be observed.

A summary of maximum CTCAE grade at patient level will be reported by treatment group. The incidence of TEAEs in each treatment arm will also be presented by SOC and PT. For each PT the grouping by severity according to the CTCAE grade (maximum grade in case of multiple AEs with same preferred term) will be reported.

11.2.5. Summaries of Adverse Events by Maximum relationship to the study treatment

At individual patient level the highest level of relationship experienced by a patient at any point in the treatment, irrespective to the AEs, will be presented.

For summaries presenting AEs related to study drug, the number of patients with an AE, is the number of patients who have each level of relationship as the highest level of relationship for the specific PT.

11.2.6. Summaries of TEAEs of Special Interest

A table presenting details of the Treatment-emergent AEs of special interest will be provided by treatment arm. TEAESI will be also listed separately.

11.3. Laboratory Data

For continuous clinical laboratory results (hematology and biochemistry parameters), the absolute value and change from baseline will be summarized by parameter and visit using descriptive statistics for the Safety Set. For laboratory parameters where the shifts to the last assessed value are evaluated, change from baseline to the last value assessed will be summarized as well.

If the value is below the lower limit of quantification (e.g.: "< X.X"), then half the lower limit of quantification will be used in the summary tables to calculate the descriptive statistics. If the value is above the upper limit of quantification (e.g.: (e.g.: "> X.X"), then the upper limit of quantification (e.g.: (e.g.: "> X.X"), then the upper limit of quantification will be used in the summary tables to calculate the descriptive statistics. In the listings, values will be listed as collected without the imputation applied.

Shift tables from baseline to the Last Value according to NCI CTCAE V5.0 grade (published on Nov 2017) will be provided for selected chemistry parameters (ALT, AST, total bilirubin, ALP, creatinine, and glucose) and hematology parameters (hemoglobin, platelet count, white blood cells, and neutrophils).

Frequency tables according to NCI CTCAE worst grade over time will be provided for ALT and AST.

In addition, % change from baseline by visit will also be measured for HbA1c and prealbumin.

Urinalysis

Business & Decision

Life Sciences

Urinalysis parameters (WBC, Erythrocytes, Protein, Glucose and Bacteria) will be classified as normal or abnormal and will be summarized by parameter using the number and percentage of subjects in each category for the Safety Set.

Shift tables from baseline to the Post-baseline Values will be presented. For WBC and Erythrocytes, values classified as High or Low will be recoded to Abnormal to be presented using the same layout as for the other qualitative urinalysis parameters.

All clinical laboratory data will be listed, and values outside the normal ranges will be flagged.

All clinical laboratory values, abnormal clinical laboratory values, and clinically significant laboratory values (including data collected at any unscheduled assessments) will also be provided in data listings.

Pregnancy test

The results of pregnancy test by visit will be summarized with counts and percentages of patients by treatment in the ITT Set.

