8.1.2 Reporting Adverse Events

AE reporting has to be in accordance with the ICH E6 Guidance on GCP and ICH E2A Guidance on Clinical Safety Management [ICH-1997; ICH-1994].

During the course of the study, all AEs (including SAEs), irrespective of the relatedness to the study drugs, must be recorded in detail in the source records and transcribed onto the AEs pages of the eCRF. During each monitoring visit, the Investigator and the site monitor will review all AEs and perform Source Data Verification (SDV). The Investigator will be responsible for ensuring that the correct information concerning all AEs is entered on the appropriate eCRF pages.

In case clinically significant laboratory abnormalities are detected, the etiology of the abnormality should be identified, and the diagnosis should be recorded as an AE. Otherwise, if the etiology cannot be identified, the laboratory abnormality as such should be recorded as the AE.

Similarly, clinically significant laboratory abnormalities detected at the screening visit (before any administration of the investigational medicinal product or additional non-investigational drug), if not justified by an underlying disease already recorded in the medical history, are to be recorded as AEs.

The reporting period for AEs is the period starting from the time of Informed Consent signature and lasting until Day 183 (+3) days post study drug administration on Day 1. All unresolved AEs (including SAEs) will be documented on the eCRF as "ongoing".

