Shift tables from baseline to the worst post-baseline results will be provided for the ECG overall interpretation. ECG measurements (HR, QT, QTcF, PR, RR, and QRS) will be summarized by treatment group and visit. Outliers' analysis will be conducted.

Shift tables from baseline to the Last Value according to NCI CTCAE grade will be provided for selected chemistry parameters (ALT, AST, total bilirubin, ALP, creatinine, and glucose) and hematology parameters (hemoglobin, platelet count, white blood cells, neutrophils, and ANC). In addition, a change and % change from baseline will also be measured for HbA1c and pre-albumin.

The best overall tumor responses will be summarized by treatment group with frequencies and percentages.

Overall survival will be described using Kaplan-Meier estimates.

Individual subject listing for all data will be provided.

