A patient will be defined as having "completed" 24 weeks treatment when the patient received study drug at the day of Visit 10 (either on-site or at home) and have evidence of treatment for all previous weeks.

Fluid retention

Presence of fluid retention will be assumed when either a treatment emergent AE associated with fluid retention is present or edema is recorded in the CRF by investigator at time of the assessment of weight. Specific assessments are scheduled at each study visit.

After a specific review of the LLTs during the BDRM, AEs coded with the following PTs were confirmed as possibly impacting the weight measurements: 'Fluid retention', 'Ascites', 'Pleural effusion', 'Oedema peripheral', 'Oedema'. These AEs will be taken into account.

Clinically meaningful thresholds for 5-IASS change and Body Weight Change

To support with patient informed interpretation of meaningful change or stabilization, the results of a quantitative analysis of a separate study (7), combined with evidence from the embedded qualitative interview sub-study (6), support a responder definition of 3.0 for the 5-IASS Score and 1.5 kg weight gain for body weight.

These thresholds were defined in line with FDA guidance, therefore anchor-based methods for score interpretation were considered the primary analysis. Distribution-based methods were used as supportive and secondary analysis using PGIS (Patient Global Impression of Severity) and PGIC (Patient Global Impression of Change) as anchors.

For the analysis of the duration of treatment benefit the definition of a threshold to establish a change from baseline as clinically meaningful is provided (Sections 10.2 and 10.2.1)

Last value

Business & Decision

Life Sciences

For Laboratory Shift Tables analysis, the Last Value is the last value reported by the patient during the study period.

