11.5. Electrocardiogram (ECG)

Life Sciences

Business & Decision

Shift tables from baseline to the worst post-baseline results will be provided for the ECG overall interpretation. The following categories will be used: normal, abnormal and not clinically significant, abnormal and clinically significant. The frequencies of ECG overall interpretation by visit as well as the number and percentage of patients who performed the assessment will be also tabulated.

ECG measurements (HR, QT, QTcF, QTcB, PR, RR, and QRS) will be summarized using descriptive statistics by treatment group and visit. The change from baseline will also be summarized in the same manner.12-lead ECGs measurements are obtained in triplicate. Analysis will be performed using the average of the three measurements. In case of one or two measurements are missing the average will be calculated on the bases of the available measurements. Summaries showing the number and percent of patients with outlier values will be presented by treatment.

ECG interval	Categorical outlier criteria
QTcF	Treatment-emergent value of > 450 and ≤ 480 ms when not present at baseline (new onset)
	Treatment-emergent value of > 480 and ≤ 500 ms when not present at baseline (new onset)
	Treatment-emergent value of > 500 ms when not present at baseline (new onset)
	Increase of QTcF from baseline of > 30 and \leq 60 ms
	Increase of QTcF from baseline > 60 ms
PR	Increase of PR from baseline > 25% resulting in PR > 200 ms
QRS	Increase of QRS from baseline > 25% resulting in QRS > 120 ms
HR	Decrease of HR from baseline >25% resulting in HR < 50 bpm
	Increase of HR from baseline >25% resulting in HR > 100 bpm

Outlier values will be identified using the following criteria:

Any treatment emergent clinically significant ECG abnormality will be reported as an AE.

All ECG data will be listed by patient.

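### For eight of the ten CTCAE-graded laboratory parameters, glucose included, the only graded table is baseline to last value, so an abnormality that resolves earlier is in no graded laboratory table

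*SAP*

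**What the plan says.** SAP section 11.3 lists six chemistry parameters (ALT, AST, total bilirubin, ALP, creatinine, glucose) and four haematology parameters (haemoglobin, platelets, white cells, neutrophils) for "Shift tables from baseline to the Last Value according to NCI CTCAE V5.0 grade". Protocol section 9.4.6 has the same rule: "Shift tables from baseline to the Last Value according to NCI CTCAE grade". SAP section 8.8 defines the term for these tables: "the Last Value is the last value reported by the patient during the study period".

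The same SAP section then adds: "Frequency tables according to NCI CTCAE worst grade over time will be provided for ALT and AST". It plans no other graded laboratory table. The remaining blood outputs are ungraded: descriptive statistics by visit, change to the last value, percentage change for HbA1c and pre-albumin, and listings flagged against normal ranges.

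Elsewhere the SAP summarises safety by the worst result. Section 11.5 says "Shift tables from baseline to the worst post-baseline results will be provided for the ECG overall interpretation", and in section 11.2.4 "the maximum CTC grade describes the worst grade experienced by a patient at any point in the treatment".

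**The concern.** A last-value shift shows which abnormalities were still present at the end of observation. It does not show how many patients ever reached a given grade. For ALT and AST the extra table supplies that count; for the other eight parameters nothing does, and the SAP gives no reason for the difference.

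Glucose is the main case. The ninth AESI in SAP section 11.2.2 begins "Hyperglycemia (CTCAE Grade" and sets the cut at grade 3 or above. Protocol section 1.3 also reports that adverse drug reactions related to raised blood glucose were frequent in two earlier studies, although it says no event indicated a significant risk. Of the three AESIs that rest on a laboratory value (AST, ALT, glucose), only glucose has no worst-grade laboratory table.

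At stake is a by-arm count of peak laboratory grade that does not depend on whether the investigator chose to report an adverse event. No efficacy result or error rate is involved.

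**Working it through.** **Coverage count** (inputs: SAP section 11.3)

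- Parameters with a graded shift to last value: 6 chemistry + 4 haematology = 10.
- Parameters with a worst-grade table: 2 (ALT, AST).
- Parameters with only the last-value graded table: 10 − 2 = 8, glucose among them.

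**Draws used** (inputs: protocol sections 7.2.6.1 and 7.2.6.2)

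Haematology and chemistry are drawn at every visit, which gives 8 scheduled post-baseline draws (Weeks 3, 6, 9, 12, 15, 18, 21, 24). For a patient who attends them all, the shift table uses 1. The grades at the other 8 − 1 = 7 enter no graded laboratory table for these eight parameters.

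**Illustration of size**

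The plan states no figure to reproduce, and it gives no laboratory toxicity rates or durations. The following rests on assumptions. Suppose a patient has k post-baseline draws, and a graded excursion starts at one of them with equal probability and lasts m consecutive draws (m ≤ k), or until the last draw if that comes first. It is still present at the last draw only if it started in the last m. So

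P(not seen at last value) = 1 − m/k.

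| k | m = 1 | m = 2 | m = 3 |
|---|---|---|---|
| 8 | 1 − 1/8 = 87.5% | 1 − 2/8 = 75% | 1 − 3/8 = 62.5% |
| 4 | 1 − 1/4 = 75% | 1 − 2/4 = 50% | 1 − 3/4 = 25% |
| 2 | 1 − 1/2 = 50% | 1 − 2/2 = 0% | n/a |

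The SAP reports 318 patients randomised 1:1, so about 318/2 = 159 per arm. With an assumed 5% having such an excursion, 159 × 0.05 = 8.0 patients would appear in a worst-grade table. The last-value table would show:

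- k = 8, m = 1: 8.0 × 1/8 = 1.0
- k = 8, m = 2: 8.0 × 2/8 = 2.0
- k = 4, m = 2: 8.0 × 2/4 = 4.0
- k = 4, m = 3: 8.0 × 3/4 = 6.0
- k = 2, m = 2: 8.0 × 2/2 = 8.0

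The range over the grid is therefore 1 to 8 of 8. At an assumed 2% the worst-grade count is 159 × 0.02 = 3.2 and the last-value count 0.4 to 3.2. At 10% they are 15.9 and 2.0 to 15.9. Under-counting is greatest for short excursions in patients with many draws.

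**Other routes for a resolved abnormality**

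- *Adverse events.* Protocol section 8.1.2: "In case clinically significant laboratory abnormalities are detected, the etiology of the abnormality should be identified", with the diagnosis then recorded as the event, or the laboratory finding itself if no cause is identified. This reaches the graded adverse event tables, but only after a judgement of clinical significance.
- *By-visit statistics.* SAP section 8.1 includes the minimum and maximum. These show one extreme value per visit and arm, not how many patients reached each grade.
- *Listings.* All values are listed and out-of-range values flagged. No grade or by-arm count is promised.

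**The case against.** The strongest case against is that this is a reporting preference.

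- **Glycaemic safety has other outputs.** HbA1c is measured at screening and Weeks 12 and 24, and urine glucose at screening and Weeks 9 and 24 with shift tables. Neither depends on adverse event reporting. Hyperglycaemia of grade 3 or higher that is reported goes into an AESI table. This stands as mitigation, but none of these outputs gives a peak blood glucose grade by arm independent of investigator judgement.
- **Few draws are likely after drug stop.** SAP section 8.3.1 says few retrieved dropouts were available. An abnormality present when a patient stops will then often be the last value and be tabulated. This stands: the loss falls mainly on abnormalities that resolve while the patient continues in the study.
- **The eight parameters are not equally important.** Transaminases and blood glucose are the laboratory signals that the protocol names, and no haematology parameter, ALP or creatinine is an AESI. That supports putting glucose first. It does not explain why glucose was left out.
- **The mock tables were not available.** SAP section 12.5 places them in a separate document. They might contain more, but the SAP text commits to no further graded laboratory table, and the text should state what is planned.
- **The illustration is hypothetical.** True. The finding rests on the structure of the tables, not on those counts.
- **No data are lost.** Also true: the tables could be produced at any time. That makes the change cheap, and specifying it in the SAP fixes the rules before the results are seen.

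**Conclusion.** The point holds. On the SAP text, 8 of 10 graded parameters have no table that counts peak grade by arm, and glucose is one of them despite being the basis of an AESI. The rule also departs from the SAP's own practice for ALT and AST, ECG interpretation and adverse event severity.

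The size cannot be taken from the documents. Under the stated assumptions (uniform onset, fixed duration, 5% of 159 patients per arm), the last-value table would show anywhere from 1 to all 8 affected patients. Abnormalities that persist to the last draw are counted either way.

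The consequence is confined to descriptive safety reporting. The change should be made, but no confirmatory conclusion turns on it.

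**What to change.** In SAP section 11.3, add shift tables by arm from baseline to the worst post-baseline CTCAE grade. At minimum, extend the planned ALT and AST worst-grade frequency table to the other eight parameters, starting with glucose.

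Two rules need stating so that the tables can be reproduced:

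- **Window.** Use the SAP's own treatment-emergent window from section 11.2.1: up to study completion, or up to 14 days after treatment discontinuation.
- **Unscheduled draws.** State that they count towards the worst grade. Section 11.3 mentions them only for the listings.

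Keep the last-value shift as a supplementary table, and record the addition in SAP section 13, where other laboratory summaries have already been added to the protocol's plan.

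The cost is a few descriptive tables from data already collected, reusing the program planned for ALT and AST. No planned table is lost.
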